
Outcome measures section below.

Randomisation

Randomisation of schools to one of the two treatment arms took place on the 29th September 2021. In total, 201 schools were randomised to either the intervention or control group. Randomisation was conducted in Stata by a member of the evaluation team who was not blind to school identities, however, to verify independence, the randomisation code and outcome was checked by an independent staff member who was not part of the evaluation team. The randomisation was stratified by TL region with schools as the unit of randomisation, and (Year 3) pupils as the unit of analysis. A tailored package in Stata (`randtreat`) was used to implement the cluster randomisation with regional stratification. The code used to randomise schools as well as all relevant variables has been saved and can be made available if requested. This code will be included in the final Evaluation Report at the conclusion of the study. The allocation was recorded in Excel and communicated to the implementation team.

As specified in the Evaluation Protocol, randomising at the school level was perceived to reduce the chances of contamination between randomised groups as TAs would be delivering to all identified children in the school. Furthermore, regional stratification was deemed appropriate given the regional nature of delivery, with one TL delivering the training in each region (hence why we refer to 'TL regions'). Regions included in the randomisation as stratifiers were: Cambridgeshire, Derbyshire, Devon, East Sussex, Essex, Greater Manchester, Merseyside,² Nottinghamshire, South Yorkshire, Suffolk, West Sussex, West Yorkshire.

Randomisation occurred with a 50:50 allocation to treatment and control. Schools allocated to treatment receive IWM+A training and are expected to deliver the IWM+A intervention, while schools allocated to control are expected to carry on with business as usual (BAU), and do not receive the training. Schools assigned to the control group will be given £1,000 on completion of all endline assessments. These funds are to be used at the discretion of the school and could be used to buy an intervention programme of their choice, including IWM+A from September 2022. The value of the incentive is the same as was used in the efficacy trial.

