Table 2 shows the actual allocations for the overall sample of participating schools and by TL region. In total, 101 schools were allocated to the control condition. A total of 100 schools were allocated to the intervention group. The numbers of schools in the trial varied by the stratification regions, between nine schools in Devon and 24 in South Yorkshire. The randomisation produced as equal an allocation to the intervention and control group as possible among the overall sample of participating schools and across the TL regions. For instance, in Devon, five of the nine schools in the stratum were allocated to the control group, and four were allocated to the Intervention group. In South Yorkshire, an equal number of schools (12) were allocated to each condition.

Table 2. IWM+A randomisation results

² Table 2 refers to two Merseyside TL regions as there are two TLs delivering the training in this area.

		Control group	Intervention (IWM+A) group	Total schools
1	Cambridgeshire	9	9	18
2	Derbyshire	8	8	16
3	Devon	5	4	9
4	Essex & Suffolk	9	9	18
5	Greater Manchester	11	11	22
6	Merseyside (LB)	9	10	19
7	Merseyside (LLS)	9	9	18
8	Nottinghamshire	10	10	20
9	South Yorkshire	12	12	24
10	Sussex	9	8	17
11	West Yorkshire	10	10	20
	Total	101	100	201

Of the 201 schools that were randomised on 29th September 2021 as above, 195 nominated and provided baseline data for all ten selected pupils. Of the 6 schools not providing full data prior to randomisation, 4 schools had nominated and provided baseline data for nine out of ten pupils, while one school did so for six out of ten pupils and the final remaining school did so for four out of ten pupils. Thus, at baseline, the effective sample size was 1,996 pupils out of a theoretical population of 2,010 (201 schools multiplied by ten nominated pupils).

Outcome measures

Baseline measures

Baseline assessment for trial participating pupils *only* will consist of the following tests:

- 1) **Maths Attainment** based on the Early Years Foundation Stage Profile (EYFSP) Numbers, and Shape, Space and Measures subtests.
- 2) **Attention and Behaviour** based on the adapted 15-item SNAP-IV Teacher Attention Rating Scale (Bussing et al., 2008; Swanson et al., 2001).

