Table 3. Power Calculations

		Protocol				Randomisation	
		UPPER		LOWER		OVERALL	FSM
		OVERALL	FSM	OVERALL	FSM		
Minimum Detectable Effect Size (MDES)		0.172	0.221	0.188	0.242	0.188	0.231
Pre-test/post-test correlations	level 1 (pupil)	0.50	0.50	0.50	0.50	0.50	0.50
	level 2 (class)	NA	NA	NA	NA	NA	NA
	level 3 (school)	0	0	0	0	0	0
	level 2 (class)	NA	NA	NA	NA	NA	NA

⁴ It should be noted that the efficacy trial used KS1 arithmetic scores as baseline, as opposed to EYFSP suggested here. This was used as the assumption for the correlation in the power calculations as there is no currently published data on EYFSP and BAS3 correlations.

		Protocol				Randomisation	
		UPPER		LOWER		OVERALL	FSM
		OVERALL	FSM	OVERALL	FSM		
Intracluster correlations (ICCs)	level 3 (school)	0.16	0.16	0.16	0.16	0.16	0.16
Alpha		0.05	0.05	0.05	0.05	0.05	0.05
Power		0.8	0.8	0.8	0.8	0.8	0.8
One-sided or two-sided?		Two	Two	Two	Two	Two	Two
Average cluster size		10	3	10	3	10	4
Number of schools	intervention	120	120	100	100	100	94
	control	120	120	100	100	101	95
	total	240	240	200	200	201	189
Number of pupils	intervention	1,200	360	1,000	300	992	403
	control	1,200	360	1,000	300	1,004	401
	total	2,400	720	2,000	600	1,996	804

At randomisation stage, there were 201 schools and a total of 1,996 pupils with baseline data. This represents an average of 9.93 (10) pupils per school. Assuming the same parameters as at protocol stage and given the achieved overall sample, the MDES is $d=0.188$. As such, the MDES for the overall sample as reported in the SAP is the same as the lower bound MDES as reported at protocol stage ($d=0.188$).

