To assess whether there are systematic differences between those who drop out and those who do not – and thus whether these factors should be included in analysis – we will model missingness at follow-up (defined as pupils with missing primary outcome data at endline) as a function of baseline covariates, including treatment. The analysis model for this approach will mirror the multilevel level model specified in Equation (1), with pupils clustered in classes, but the outcome will be a binary variable identifying missingness (where 1=missing; 0=complete) in a multilevel mixed-effects logistic regression model (using Stata's `meLogit` command). We can similarly model missingness at baseline (defined as pupils with missing baseline data, namely missing EYFSP) as a function of endline covariates, including treatment.

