We will follow the protocol for missing data suggested by the EEF (see EEF, 2018). For less than 5% missingness overall from randomisation to final analysis, a complete-case analysis will be employed. This assumes that data are missing completely at random (MCAR), which we will be able to test partially with the model outlined above. For more than 5% missing data overall from randomisation to final analysis, our approach will depend on pattern of missingness. If the pattern of missingness may be unrelated to the treatment effect (e.g., pupil illness, staff changes or COVID-related impacts on testing but not on intervention), then missing data will be assumed MCAR and we will continue with a complete-case analysis. Otherwise, we will adopt a full-information maximum likelihood (FIML) approach. FIML estimates the value of the trial parameter of interest (τ in Equation 1) by maximising the likelihood function in the presence of missing data. We will not supplement this analysis with a separate approach, usually multiple imputation, MI, analysis, as the results of the two have been shown recently to be broadly equivalent (Lee & Shi, 2021). Additionally, in comparison to MI, FIML produces the same results every time, can be estimated in a single model and simulation studies show that it can reduce bias as well as MI (for a detailed discussion of FIML vs MI see Allison, 2012 or Jakobsen et al, 2017). The FIML approach only alleviates bias if pattern of missingness is dependent only on observed variables, namely missing at random (MAR); if the reason for missingness is due to unobserved variables, namely missing not at random (MNAR), then FIML or MI will not improve estimates. Note, however, that MAR and MNAR are not distinguishable based on observed data. If it seems likely data could be MNAR, sensitivity analysis will be conducted and reported alongside headline estimates.

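### Below 5% overall missingness the SAP fixes a complete-case analysis whatever the split between arms, although the only completion-linked payment it states goes to control schools

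*SAP*

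**What the plan says.** On incentives, the SAP's Randomisation section says: "Schools assigned to the control group will be given £1,000 on completion of all endline assessments". Of the other arm it says: "Schools allocated to treatment receive IWM+A training and are expected to deliver the IWM+A intervention". It mentions no payment to intervention schools for completing endline, and does not say that there is none.

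On missing data, the lower branch reads: "For less than 5% missingness overall from randomisation to final analysis, a complete-case analysis will be employed". The SAP adds: "This assumes that data are missing completely at random (MCAR), which we will be able to test partially with the model outlined above". The upper branch reads: "For more than 5% missing data overall from randomisation to final analysis, our approach will depend on pattern of missingness". In that branch, missingness that may be unrelated to the treatment effect still leads to complete cases under MCAR; otherwise FIML is used.

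The same section plans to tabulate attrition by arm and to fit a multilevel logistic model for missingness with treatment among the predictors. Missingness at follow-up is counted by pupil: "defined as pupils with missing primary outcome data at endline". It also promises a sensitivity analysis if MNAR seems likely, without giving a method or saying what would make it seem likely.

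**The concern.** A total of 5% says little about bias in a two-arm comparison. What matters is whether the pupils lost from one arm differ from those lost from the other, and a low total can hide loss that falls almost wholly on one side.

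The SAP gives a reason to expect that. Control schools receive £1,000 only if they finish endline. Intervention schools receive training before delivery, which runs from October 2021 to February 2022, while endline is in May 2022. On what the SAP states, only control schools still have a benefit that depends on finishing.

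The planned diagnostics would show an imbalance, but in the lower branch no action is tied to them. The primary intention-to-treat estimate could then rest on MCAR after the trial's own missingness model had given evidence against it.

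**Working it through.** **Inputs.** From Randomisation, including Table 2: "In total, 101 schools were allocated to the control condition. A total of 100 schools were allocated to the intervention group". From Sample size and power calculations overview: "At randomisation stage, there were 201 schools and a total of 1,996 pupils with baseline data". Table 3 divides the pupils into 992 intervention and 1,004 control. It gives ICC 0.16, pre-post correlation 0.50 (level-1 R² = 0.25), two-sided alpha 0.05, power 0.8, cluster size 10 and an overall MDES of 0.188.

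**The plan's own figures.**
- Pupils: 195×10 + 4×9 + 6 + 4 = 1,996, as stated.
- MDES = M × √[ICC/(P(1−P)J) + (1−ICC)(1−R²)/(P(1−P)Jn)], with M = t(0.975, J−2) + t(0.80, J−2), J = 201, n = 10, P = 0.5.
- The terms under the root are 0.16/50.25 = 0.00318 and 0.63/502.5 = 0.00125. With M about 2.815, the MDES is 0.188, as stated.

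**What fits under the cut.** 5% of 1,996 is 99.8 pupils, so the lower branch allows at most 99 missing. If all 99 were in the intervention arm, that arm would lose 99/992 = 10.0% and control 0%.

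| Intervention schools lost (control 0, no other loss) | Pupils | Overall | Intervention arm | Branch |
|---|---|---|---|---|
| 9, all with ten pupils | 90 | 90/1,996 = 4.51% | 90/992 = 9.1% | complete case, automatic |
| 10, one with nine pupils | 99 | 99/1,996 = 4.96% | 10.0% | complete case, automatic |
| 10, all with ten pupils | 100 | 100/1,996 = 5.01% | 10.1% | depends on pattern |

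Ten schools sit on the cut, so the nine-school case is the safe illustration.

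**Size of the shift.** Let f be the fraction of the intervention arm lost, and let d be how far the lost pupils would have scored below those retained, in SD units. The full-arm mean is the retained mean minus f×d, so with no control loss the complete-case effect is too high by f×d. The SAP gives no value for d; the range 0.25 to 0.5 is an assumption.
- d = 0.25: 0.0907 × 0.25 = 0.023 SD; 0.023/0.188 = 12%.
- d = 0.5: 0.0907 × 0.5 = 0.045 SD; 0.045/0.188 = 24%.

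**With ordinary loss as well.** Suppose 3% of pupils are missing at random in both arms (assumption): 0.03 × 1,996 ≈ 60. That leaves 99 − 60 = 39 pupils under the cut. If all 39 are extra intervention losses, the gap between arms is 39/992 = 3.9 points and the shift is 0.039 × 0.25 to 0.039 × 0.5, about 0.01 to 0.02 SD.

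**The case against.** **Payment.** A reader might infer that intervention schools are paid nothing. The SAP is silent, and such terms are commonly left to the protocol, which was not available for this review. The £1,000 can also be read as offsetting the control schools' lack of training. So the SAP does not establish which arm would lose more schools. The gap in the decision rule does not depend on this: it would remain if both arms were paid alike.

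**Existing safeguards.** A reader might also infer that the plan ignores differential attrition. It does not. It examines attrition by arm, models missingness on treatment in order to judge what belongs in the analysis, lets the pattern matter above 5%, and mentions an MNAR sensitivity analysis. This stands, and it narrows the point to the lower branch and the undefined trigger. But the stated purpose of the missingness model is not a rule. Treatment is already in Equation 1, so finding that it predicts missingness leaves nothing to add unless a further step is written down.

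**Size and direction.** Stopping delivery is not the same as missing endline, because the intention-to-treat analysis keeps pupils whose schools withdraw from delivery. If lost schools differed only through poor delivery, their shortfall could hardly exceed the treatment effect. At the efficacy estimate of 0.24 the nine-school shift would be 0.0907 × 0.24 = 0.022 SD, and nil if the intervention has no effect. The upper end of the range needs lost schools to be weaker for other reasons too. A claim that the estimate will be biased in favour of IWM+A is therefore not supported.

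**Guidance.** The SAP says that its approach follows funder guidance, which cannot be checked here. A by-arm condition adds to the 5% rule and does not remove it.

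**Conclusion.** The point holds for the branch below 5%: complete-case analysis under MCAR is fixed by the overall total, no consequence is attached to an association between arm and missingness, and the MNAR analysis has neither trigger nor method. A split of about 9% against 0% can pass through it.

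The illustrated shift of 0.023 to 0.045 SD rests on three assumptions: one-sided loss of nine full schools, no other missing data, and lost pupils 0.25 to 0.5 SD below those retained. With 3% ordinary loss in both arms it falls to about 0.01 to 0.02 SD. This is worth guarding against in an effectiveness estimate, but it does not undermine the design. The payment makes differential loss foreseeable; it does not show that loss will occur or which way it would bias the result.

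**What to change.** Amend the SAP's Missing data section before endline data are seen.

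1. Apply the 5% threshold within each arm as well as overall.
2. If either arm exceeds it, or the missingness model shows an association with treatment, do not rely on MCAR. State in advance what counts as an association.
3. In that case refit the primary model with baseline SNAP-IV, age and gender as auxiliary variables, and FSM once it arrives from the NPD. In Table 4 SNAP-IV and gender are complete and age is missing for two pupils. Auxiliary variables are needed because, when only outcomes are missing, FIML with just the Equation 1 covariates adds almost nothing to complete cases.
4. Pre-specify a delta-shift (MNAR) sensitivity analysis that lowers the missing intervention-arm BAS3 scores in steps until the conclusion changes, and report the shift at which it does.
5. Confirm what each arm was paid for completing endline, and report it by arm.

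The cost is SAP wording and one extra sensitivity analysis, with no new data collection and no change to payments. It will be triggered somewhat more often: 50 missing intervention pupils (50/992 = 5.04%) would be enough, even with none missing in control (50/1,996 = 2.5% overall).

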Attention and behaviour outcomes will be measured using the SNAP-IV Teacher Attention Rating Scale. As outlined in the theory of change (see Figure 1 in the IWM+A protocol), attention in class is considered to be an important proximal outcome leading to improved impact in maths. Further details on this measure can be found under Baseline measures.

The scale needs to be completed by an individual (i.e. a teacher) who is familiar with the pupil and their behaviour, and as such will be completed by pupils' teachers, who will consequently not be blind to allocation. Teachers will be asked to complete these measures for all nominated pupils in May 2022.

Sample size and power calculations overview

The initial power calculations in the Protocol (Brown et al., 2021) were based on both the information provided in the Invitation to Tender and the subsequent set-up meetings with the Delivery team and the EEF. Power and minimum detectable effect size (MDES) calculations were performed using the PowerUp! Tool (Dong & Maynard, 2013).

At protocol stage, upper and lower bound MDESs were calculated using a two-level random assignment assuming equal allocation to the intervention and control groups. The upper bound MDES calculations were based on assumed sample sizes of 240 schools equally allocated across intervention and control, with 10 pupils entered into the trial per school. The lower bound MDES calculation assumed sample sizes of 200 schools again equally allocated across treatment and control, with 10 pupils entered into the trial per school.

Based on the efficacy trial, we assumed the proportion of variance in level 1 outcomes explained by level 1 covariates R^2 was 0.25, equating to a pre-post-test correlation of 0.5, as per Table 3 (Wright et al., 2019).⁴ We used two-level clustered designs and based our calculations on an intra-cluster correlation (ICC) of 16 per cent (0.16, as per Table 3).

Assuming a desired power of 80 per cent, alpha of 5 per cent, a continuous, normally distributed outcome as well as taking all other assumptions outlined above and in Table 3, the overall upper bound MDES calculation at protocol stage was $d=0.172$, while the lower bound MDES calculation was $d=0.188$. Using the same parameters and assuming that on average 3 FSM-eligible pupils per school would be entered into the trial (a rate of 30% FSM-eligibility), the upper bound MDES at protocol stage was $d=0.221$ while the lower bound MDES was $d=0.242$.

Table 3. Power Calculations

		Protocol				Randomisation	
		UPPER		LOWER		OVERALL	FSM
		OVERALL	FSM	OVERALL	FSM		
Minimum Detectable Effect Size (MDES)		0.172	0.221	0.188	0.242	0.188	0.231
Pre-test/post-test correlations	level 1 (pupil)	0.50	0.50	0.50	0.50	0.50	0.50
	level 2 (class)	NA	NA	NA	NA	NA	NA
	level 3 (school)	0	0	0	0	0	0
	level 2 (class)	NA	NA	NA	NA	NA	NA

⁴ It should be noted that the efficacy trial used KS1 arithmetic scores as baseline, as opposed to EYFSP suggested here. This was used as the assumption for the correlation in the power calculations as there is no currently published data on EYFSP and BAS3 correlations.

		Protocol				Randomisation	
		UPPER		LOWER		OVERALL	FSM
		OVERALL	FSM	OVERALL	FSM		
Intracluster correlations (ICCs)	level 3 (school)	0.16	0.16	0.16	0.16	0.16	0.16
Alpha		0.05	0.05	0.05	0.05	0.05	0.05
Power		0.8	0.8	0.8	0.8	0.8	0.8
One-sided or two-sided?		Two	Two	Two	Two	Two	Two
Average cluster size		10	3	10	3	10	4
Number of schools	intervention	120	120	100	100	100	94
	control	120	120	100	100	101	95
	total	240	240	200	200	201	189
Number of pupils	intervention	1,200	360	1,000	300	992	403
	control	1,200	360	1,000	300	1,004	401
	total	2,400	720	2,000	600	1,996	804

At randomisation stage, there were 201 schools and a total of 1,996 pupils with baseline data. This represents an average of 9.93 (10) pupils per school. Assuming the same parameters as at protocol stage and given the achieved overall sample, the MDES is $d=0.188$. As such, the MDES for the overall sample as reported in the SAP is the same as the lower bound MDES as reported at protocol stage ($d=0.188$).

As also shown in Table 3, the number of schools with at least one FSM-eligible pupil at randomisation stage was 189 out of the 201 schools, with a total of 804 FSM pupils in the sample almost equally balanced across the intervention and control group (403 and 401 FSM pupils respectively). This represents an average of 4.25 (4) FSM pupils per school. Assuming the same parameters as at protocol stage and given the achieved sample of FSM pupils, the estimated MDES is $d=0.231$. This is roughly at the mid-point between the lower bound MDES for the FSM sample as estimated ($d=0.242$) and the upper bound MDES estimate ($d=0.221$) at protocol stage. This is likely due to the slightly higher rate of FSM eligibility (40.3%) as compared to the estimation at protocol stage (30%), despite the overall sample size aligning more with the lower bound MDES scenario. As such, the study should be powered to detect any meaningful difference for the FSM subgroup.

We acknowledge that the pre-post-test correlation is likely to be an overestimate, however, as there are no published correlations between BAS3 and EYFSP we have used data from the previous trial. To provide a more conservative estimate we have also run the power calculations with the assumption that there is no correlation. If the EYFSP is not correlated with outcome measures (i.e., pre-post-test correlation is equal to 0), the study will still be powered to detect an effect of 0.196 on all pupils, and 0.249 on FSM pupils.

Analysis

Primary outcome analysis

RQ1: What is the difference in number skills measured by the number skills subtest of the British Ability Scales (BAS3) of pupils in schools receiving IWM+A in comparison to those pupils in control schools receiving business as usual?

To address RQ1 this evaluation will use the age-standardised scores on BAS3 as a primary outcome for number skills, with prior attainment being accounted for by EYFSP scores (see Of the 201 schools that were randomised on 29th September 2021 as above, 195 nominated and provided baseline data for all ten selected pupils. Of the 6 schools not providing full data prior to randomisation, 4 schools had nominated and provided baseline data for nine out of ten pupils, while one school did so for six out of ten pupils and the final remaining school did so for four out of ten pupils. Thus, at baseline, the effective sample size was 1,996 pupils out of a theoretical population of 2,010 (201 schools multiplied by ten nominated pupils).

Outcome measures section for more detail on the BAS3 and EYSFP). The pupil level BAS3 scores will be age-standardised with a mean of 100 and standard deviation of 15.

To address the primary research question an intention-to-treat (ITT) analysis will be undertaken using multi-level modelling (MLM) with fixed effects and random intercept. In ITT, data is analysed according to the group randomised, regardless of whether the treatment was actually received as intended, and irrespective of withdrawal from the intervention post-randomisation, or deviations in programme implementation. This principle is key in ensuring an unbiased analysis of intervention effects and is in line with the EEF's guidance (see EEF 2018).

To account for the nested nature of the data, a hierarchical linear model with two levels (school, pupil) will be fitted controlling for pre-intervention scores at the pupil level. Following the stratified randomisation, the model will include a term identifying the regions (strata).

Impact will be estimated by fitting the model in equation (1). Equation (1) is known as a 'random intercepts' model because $\beta_{0j} = \beta_0 + u_j$ is interpreted as the school-specific intercept for school j and $\beta_{0j} \sim i.i.d. N(\beta_0, \sigma_u^2)$ is random (it is a number that can take any value):

$$(1) \quad Y_{ij} = \beta_0 + IWMA_j \tau + Z_j \beta_1 + X_{ij} \beta_2 + u_j + e_{ij}$$

Where:

Y_{ij} = BAS3 scores on the number skills subtest for child i in school j ;

β_0 = the cluster-level coefficient for the slope of a predictor on number skills;

$IWMA_j$ = a binary indicator of the school assignment to intervention [1] or control [0];

Z_j = school-level characteristics i.e. the stratifying variable of geographical location (as used for randomisation);

X_{ij} = pupil level characteristics for pupil i in school j , i.e. the pre-intervention EYFSP score;

u_j = school-level residuals and

e_{ij} = individual-level residuals.

The coefficient τ in Equation 1 above will represent the outcome of the trial, with respect to the primary outcome measure. Equation 1 will also be replicated for each of the three secondary outcome measures (see next section).

The effect size (Hedge's g) will be calculated for τ . The effect size will be standardised using unconditional variance in the denominator and confidence intervals will be reported to communicate statistical uncertainty in line with EEF guidance (see EEF 2018). This will tell us the average effect of the intervention on pupil outcomes in treatment schools compared to those in control schools.

All analyses will be run in Stata, versions 17 onwards.

Secondary outcome analysis

This effectiveness trial has three secondary outcome measures: wider math attainment; working memory; and attention and behaviour.

The secondary outcome analysis will follow the same procedures and use Equation (1) to estimate each respective secondary outcome model, as described in the primary analysis, substituting the primary outcome variable in turn with each of the secondary outcome variables.

For the secondary outcome analysis for Wider Maths and for Working Memory, the X_{ij} vector for pupil i in school j will be represented by the EYFSP score as the baseline. Whilst neither Wider Maths scores nor Working Memory are age-standardised, in the main analysis we will not include age in the pupil-level characteristics, X_{ij} , as the trial is within one year group, somewhat minimising concerns over age effects. If we expect Wider Maths or Working Memory scores to be age-correlated, this may introduce bias into the measurement of τ .⁵ As an additional sensitivity analysis, we will run the regressions with age (in months) included as a covariate in X_{ij} . We will also run a sensitivity analysis on the inclusion of EYFSP: given this was collected at the end of reception, it is possible that the correlation between EYFSP and current attainment is weaker than expected for a baseline measure, and may be introducing additional noise. For the secondary outcome analysis for Attention and Behaviour, the associated baseline measure will be used, since SNAP-IV has been administered at baseline.

Subgroup analyses

As defined in the trial protocol, we will conduct a subgroup analysis for pupils eligible for FSM, using the same model as our primary analysis (Equation 1). With this analysis we will explore differential effects of IWM+A for FSM pupils as they are considered a key target group by the EEF. We will identify FSM pupils within the sample of intervention and control schools as they are registered in the NPD, using the variable EVERFSM_6_P.⁶ Analysis will be undertaken using a binary FSM variable where FSM-eligible=1; non-FSM-eligible=0.

The study will first report mean outcomes by sub-categories of FSM-eligible children as a basic descriptive step. Then, we will enter an interaction term in Equation (1) above, to account for the FSM subgroup and treatment allocation while retaining the whole analytical sample in the model.

For the subgroup analysis, effect sizes and statistical uncertainty will be calculated and communicated as per the primary analysis (also see section on Effect size calculation).

Additional analyses

In the protocol we suggested we would use factor analysis to understand the extent to which specific factors in PtM linked to IWM+A are impacted by the intervention. However, on reflection we believe the most appropriate and robust use of the data is to use same analytical model as the primary analysis. We believe this is correct for two reasons. Firstly, the BAS3 Number Skills subscale has been developed specifically to measure number skills and it is a reliable measure of this concept, in contrast our factor scores from the PtM would be exploratory as the PtM has not been used in this way widely. Secondly, interpretation of the same concept using two different measures feels unnecessary – especially given potential issues already discussed. For these reasons we think that we should prioritise the BAS3 as our primary outcome measure and use the PtM as a secondary outcome measure focusing on wider maths attainment.

⁵ Due to randomisation, bias will only be introduced in τ if age is correlated with effectiveness of the IWM+A treatment (that is if older pupils improve more rapidly in response to the intervention). Whilst generally any omitted variable would introduce bias in all coefficient estimates, bias will not be introduced if the included variable is both uncorrelated with the omitted variable and all other covariates. By virtue of randomisation, treatment assignment should not be correlated with either school-level characteristics, Z_{ij} , or pupil-level characteristics (including age), X_{ij} . Thus the only reason τ would be biased would be if the treatment effect is correlated with age.

⁶ NPD Alias for this variable is: EVERFSM_6_P_[term][yy]. The variable indicates whether the pupil 'has ever been recorded as eligible for free school meals on Census day in any termly or annual Census (including Alternative Provision Census and PRU Census where available) in the last 6 years up to the pupil's current year (not including nursery)'.

The protocol also outlines an additional compliance analysis. This is outlined below (see [Compliance](#)).

Longitudinal follow-up analyses

Longitudinal analysis will be commissioned separately to this trial.

Balance at baseline

A well-conducted randomisation should create groups that are equivalent at baseline, with any imbalance at baseline occurring by chance (Glennerster & Takavarasha, 2013). However, to check for, and monitor, imbalance at baseline in the realised randomisation, baseline equivalence testing will be conducted at the school and pupil level.

At the school level, we will check the balance in the following variables by means of cross-tabulations and histograms that assess the distribution of each characteristic between the control and intervention groups. We will also report associated effect sizes to quantify the magnitude of any observed imbalance (for continuous measures), but will not undertake statistical testing as the initial randomisation necessarily means that any imbalance we observe is due to chance and therefore statistical tests are not appropriate:

- Ofsted ratings;
- Proportion of children eligible for FSM.⁷

At the pupil level, balance will be assessed as above but for the following characteristics:

- Gender;
- Age (in months);
- Prior attainment using the EYFSP;
- SNAP-IV Teacher Attention Rating Scale;
- FSM status for pupils.

At the time of drafting this SAP, data on both of the school level characteristics and three of the five pupil level characteristics (gender; age; SNAP-IV Teacher Attention Rating Scale) listed above are available for preliminary analysis of balance at baseline.

⁷ Variable used is PNUMFSMEVER: 'Percentage of pupils eligible for FSM at any time during the past 6 years'.

Table 4 documents the balance between schools and pupils in schools allocated to the control and intervention conditions respectively.

Looking at the two school level characteristics first,

Table 4 presents the balance across the intervention and control group with regards to Ofsted ratings and proportion of pupils eligible for FSM. With regards to Ofsted ratings, the proportion of intervention and control schools rated 'Outstanding' (14.3% and 15.0% respectively), 'Good' (67.3% and 71.0% respectively), 'Requires improvement' (13.3% and 11.0% respectively) and 'Inadequate' (5.1% and 3.0% respectively) were similar. Indeed, the largest percentage point difference was observed among schools rated 'Good', but this difference was still quite small at 3.7 percentage points.

Table 4 shows that the proportion of FSM-eligible children at the school level was similar in the intervention and control school (28.0% and 25.2% respectively) – a 2.8 percentage point difference was observed here. The assessment of these characteristics therefore suggests that, at the school level, a balanced distribution across the intervention and control groups was observed following randomisation.

The pupil level baseline characteristics also displayed a balanced distribution across the intervention and control groups. Along the lines of gender, the proportion of female and male pupils were similar in the intervention (53.0% and 47.0% respectively) and control groups (53.3% and 46.7% respectively). The distribution of pupil age in months was balanced across the intervention and control groups also; the mean age in months in the intervention group was 90.2 while this was 90.4 in the control group; or roughly 7.5 years in both groups. Finally, attention as measured by the SNAP-IV⁸ was also balanced across the intervention and control groups. The mean on the SNAP-IV was 1.14 in both groups, indicating relatively low levels of attentional difficulty on average in both groups. The absence of any meaningful imbalance at baseline in terms of attention was highlighted by the effect size estimate ($g=0.00$) here, as shown in

⁸ SNAP-IV attention ratings are as follows: 0=Not at all; 1=A little; 2=Mostly; 3=Very much. A higher score denotes greater attentional difficulty. The analysis of baseline equivalence was undertaken on continuous data as overall scores were used, derived by taking the mean across the 15-item attention scale.

Table 4.

We conclude that randomisation has resulted in intervention and control groups that are balanced and comparable based on the school and pupil level baseline characteristics available at the time of SAP drafting.

Table 4. Baseline characteristics of groups as randomised

School-level (categorical)	National-level mean	Control group		Intervention (IWM+A) group		
		n/N (missing)	Count (%)	n/N (missing)	Count (%)	
Ofsted rating						
1. Outstanding	10.5	15/100 (1)	15.0	14/98 (2)	14.3	
2. Good	65.8	71/100 (1)	71.0	66/98 (2)	67.3	
3. Requires improvement	16.4	11/100 (1)	11.0	13/98 (2)	13.3	
4. Inadequate	7.4	3/100 (1)	3.0	5/98 (2)	5.1	
School-level (continuous)		n/N (missing)	Mean (SD)	n/N (missing)	Mean (SD)	
Proportion of FSM-eligible children	25.0	101/101 (0)	25.2% (14.7)	100/100 (0)	28.0% (15.3)	
Pupil-level (categorical)		n/N (missing)	Count (%)	n/N (missing)	Count (%)	
Gender						
1. Female		535/1,004 (0)	53.3	526/992 (0)	53.0	
2. Male		469/1,004 (0)	46.7	466/992 (0)	47.0	
Pupil-level (continuous)		n/N (missing)	Mean (SD)	n/N (missing)	Mean (SD)	Effect size [95% CI]
Age (in months)		1,004/1,004 (0)	90.4 (3.8)	990/992 (2)	90.2 (3.7)	N/A
SNAP-IV Teacher Attention Rating Scale		1,004/1,004 (0)	1.14 (0.75)	992/992 (0)	1.14 (0.77)	0.00 [-0.09 - 0.08]

As data becomes available⁹ on the other characteristics of interest at baseline (additional to above table), we will assess baseline equivalence at the school level and the pupil characteristics as defined above.

In the final report, as above, we will not carry out statistical significance tests to assess balance at baseline, as the premise of statistical testing at baseline does not hold in randomised controlled trials.¹⁰ Instead, a table of the means along with distributions (for continuous variables) or counts with

⁹ EYFSP rating and FSM status will be obtained from the NPD.

¹⁰ Baseline Data. *Consort (2010)*. Retrieved 26 March (2019): <http://www.consort-statement.org/checklists/view/32-consort/510-baseline-data>

percentages (for categorical variables) will be presented, as above (Senn, 1994).¹¹ While EEF guidance for assessing balance at baseline is such that differences in pupil-level pre-tests should be reported as effect sizes, the pre-test measure in this trial that will be used here (the EYFSP) is categorical, thus Hedge's *g* is not appropriate as it relies on data being normally distributed.

Missing data

Missing data can arise from item non-response to any of the primary or secondary outcome measures, or from attrition of participants at school and pupil levels. Even though it is important to include all data, it can be problematic to apply the ITT principle if we are not able to complete follow-up testing for all randomised schools. To better understand the pattern of missing data and its impact on the analysis, we will explore the extent of missingness, and whether there is a pattern in missingness. We will analyse and report missingness for the primary outcome measure (and associated primary analysis); for the secondary outcome measures and the FSM subgroup we will report the extent of missing data using cross-tabulations but not undertake any additional analyses.

As a basic first step in the missing data analysis we will explore attrition across trial arms to assess bias (Higgins et al., 2011). We will provide cross-tabulations of the proportions of missing values on all baseline characteristics (as detailed in the previous section, at both pupil and school level), as well as on the primary outcome measure and secondary outcome measures.

